15. STUDY ADMINISTRATION	34
15.1. STUDY LEADERSHIP	34
16. CONFLICT OF INTEREST POLICY	34
17. LITERATURE REFERENCES	34
APPENDIX I – PROTOCOL REVISION HISTORY	36
APPENDIX II – NONSIGNIFICANT RISK RATIONALE	37

LIST OF ABBREVIATIONS

AE	Adverse Event				
ADE	Adverse Device Effect				
ASC	Ambulatory Surgery Center				
CFR	Code of Federal Regulations				
СМР	Clinical Monitoring Plan				
CRF	Case Report Form				
CRO	Contract Research Organization				
eCRF	Electronic Case Report Form				
EC	Ethics Committee				
EDC	Electronic Data Capture				
FDA	Food and Drug Administration				
GCP	Good Clinical Practice				
GMP	Good Manufacturing Practices				
HIPAA	Health Insurance Portability and Accountability Act				
ICH	International Conference on Harmonisation				
ICH E6	International Conference on Harmonisation Guidance for Industry, Good Clinical Practice:				
	Consolidated Guidance				
ICMJE	International Committee of Medical Journal Editors				
IFU	Instructions for Use				
IRB	Investigational Review Board				
ISO	International Organization for Standardization				
LWI	Lateral Wall Insufficiency				
MAC	Monitored Anesthesia Care				
NAO	Nasal Airway Obstruction				
NSR	Non-significant Risk				
NOSE	Nasal Obstruction Symptom Evaluation				
NVC	Nasal Valve Collapse				
OHRP	Office for Human Research Protections				
PRO	Patient Reported Outcome				
PI	Principal Investigator				
QA	Quality Assurance				
QC	Quality Control				
QOL	Quality of Life				
QSR	21CFR Part 820, Quality System Regulation				
SAE	Serious Adverse Event				
SADE	Serious Adverse Device Effect				
SAP	Statistical Analysis Plan				
SOP	Standard Operating Procedure				
UADE	Unanticipated Adverse Device Effect				
UP	Unanticipated Problem				
US	United States				
VAS	Visual Analog Scales				

STATEMENT OF COMPLIANCE

I have received and reviewed this protocol. The trial will be carried out in accordance with this protocol and Good Clinical Practice (GCP) as required by the following:

- United States (US) Code of Federal Regulations (CFR) applicable to clinical studies (45 CFR Part 46, 21 CFR Part 50, and 21 CFR Part 56, and 21 CFR Part 812.2(b)
- International Conference on Harmonisation (ICH) Good Clinical Practice E6
- ISO 14155:2011 Clinical investigation of medical devices for human subjects GCP

All key personnel (all individuals responsible in the conduct of this trial) have completed Human Subjects Protection Training.

I agree to ensure that all staff members involved in the conduct of this study are informed about their obligations in meeting the above commitments.

Investigator's Printed/Typed Name

Investigator's Signature

Date

PROTOCOL SUMMARY

Title:	Spirox Latera [™] Implant support of lateral nasal wall cartilage (LATERAL-OR) study				
Design:	A prospective, multi-center, non-randomized, single arm, controlled study				
Objectives:	To obtain outcomes data in subjects with severe to extreme class NOSE scores undergoing placement of the Spirox Latera Implant with or without concurrent septoplasty and/or turbinate reduction procedures in an operating room setting.				
Eligibility Criteria	eference Sections 5.1 and 5.2 below.				
Primary Endpoints:	Primary Efficacy Endpoint: Proportion of treatment responders at 6 months post procedure.				
	Responder is defined as subject that has at least one (1) NOSE class improvement or at least 20% NOSE score reduction				
	Primary Safety Endpoint : Nasal procedure and Latera [™] device-related adverse events through 6 months				
Secondary Endpoints:	 Proportion of treatment responders at 1, 3, 12, 18 and 24 months post procedure. Change in nasal airway obstruction from baseline to 1,3, 6, 12, 18 and 24 months as reported by subjects on the VAS scale. Subject satisfaction questionnaire at 6 months. Procedure and device-related adverse events though 24 months. 				
Exploratory endpoints:	Reference Section 4.2.3 below.				
Population:	Up to 170 subjects will be enrolled				
Number of Sites:	Approximately 25 sites in the U.S.				
Description of Device:	The Latera [™] Absorbable Nasal Implant and Delivery Device includes an absorbable implant designed to provide internal support of the upper and lower lateral nasal cartilages. The Implant absorbs over a period of approximately 18 months. The absorbable Implant is comprised of a 70:30 blend of poly(L-lactide) and poly(D-lactide). The Implant is introduced through a trans-mucosal insertion technique using a delivery device. The Implant consists of a ribbed cylindrical structure which employs a forked end to facilitate anchoring within the target tissue. The geometry of the forked end is flexible, and collapses to fit within the 16-gauge cannula portion of the delivery tool.				
Study Duration:	Approximately 36 months from when enrollment begins to completion of data analyses.				
Participant Duration:	Enrolled subjects will be followed for 24 months post-procedure				
Regulatory Status:	This study is a post-market evaluation of a 510(k) cleared, non-significant risk, medical device in commercial distribution, used according to FDA cleared indications for use				

Spirox Latera [™] implant support of lateral wall cartilage (LATERAL-OR) study
SPI-CP-301

SCHEMATIC OF STUDY DESIGN

CLINICIAL PROTOCOL

2. INTRODUCTION: BACKGROUND INFORMATION AND SCIENTIFIC RATIONALE

2.1. BACKGROUND INFORMATION

Nasal airway obstruction can be caused by several independent or concomitant factors including septal deviation, enlarged turbinates and a weakened nasal lateral wall, leading to nasal valve collapse (NVC). The nasal valve, first described in the early 20th century by Mink¹, is a complex, three-dimensional, dynamicallyalternating structure that controls nasal airflow resistance. A dysfunction of the nasal valve can lead to nasal obstruction with a significant drop in the quality of life for patients². As defined by the Hagen–Poiseuille law, the flow through a tube is proportional to the 4th power of the radius of the tube and inversely proportional to the pressure difference across the tube. Although more complex models would be required to account for turbulence and other factors, it is clear that even a small decrease in the valve area can contribute to nasal obstruction. Common causes of NVC are prior rhinoplasty, aging, nasal trauma and congenital abnormalities that weaken the nasal cartilage, leading to a lateral wall insufficiency (LWI)^{3,4}.

Therapies to correct NVC include invasive surgical procedures and non-surgical solutions to temporarily dilate the nasal valve, such as Breathe Right[®] strips or nasal cones. Surgical strategies that involve septoplasty⁵ or inferior turbinate reduction⁶ may alleviate impaired nasal breathing, but do not directly address the weakened lateral wall. Procedures intended to stabilize the lateral wall include cartilaginous grafts typically harvested from the nasal septum⁷, ear⁸ or rib cartilage⁹. These grafts can be placed as lateral crural strut grafts¹⁰, alar batten grafts¹¹ or butterfly grafts¹². Implants made from non-absorbable alloplastic materials have also been used for treatment of NVC including expanded polytetrafluoroethylene¹³ and high-density porous polyethylene¹⁴. These materials have not gained wide utilization as they require invasive surgical procedures and are associated with increased risks of infection, extrusion, and the potential need for revision procedures.

Surgery to strengthen the lateral wall has been shown to significantly improve the quality of life for subjects suffering from nasal airway obstruction¹⁵, however current procedures are generally invasive and have the potential to permanently alter the patient's appearance¹⁶. This study utilizes a minimally invasive technique to address NVC by supporting the nasal lateral wall cartilage with an absorbable implant utilized.

Spirox has developed the Latera Absorbable Nasal Implant and Delivery Device, to enable a less invasive alternative to current surgical approaches used to support weak lateral wall cartilage. This device has been cleared by the U.S. FDA via 510(k) submissions and is currently in commercial distribution. The device will be used according to the cleared indications for use in this study. This non-significant risk, post-market study seeks to obtain outcomes data in subjects with severe to extreme¹⁷ severity class NOSE scores (\geq 55), undergoing placement of Spirox Latera Absorbable Nasal Implant with or without concurrent septoplasty and/or turbinate reduction procedures in an operating room setting.

2.2. PRIOR INVESTIGATIONS

A prior study of this device was performed in the setting of an EC approved protocol in Germany. The study was conducted at three institutions under the oversight of Co-Principal Investigators, [name], MD and [name] [name] in Munchen, Germany. This prior first in man investigation evaluated the safety and performance of the Spirox device and its ability to support upper and lower lateral cartilage in subjects with nasal valve collapse as primary contributor to nasal airway obstruction (NAO) under general or local anesthesia. A brief summary of this prior investigation follows.

Spirox Latera™ implant support of lateral wall cartilage (LATERAL-OR) study	Version 2.0
SPI-CP-301	September 7, 2017

Fourteen (14) cases were performed in an operating suite under general anesthesia and sixteen (16) cases were performed in a clinic-based setting under local anesthesia. A total of fifty-six Implants were placed in thirty subjects. Subjects with a Nasal Obstruction Symptom Evaluation (NOSE) scale score \geq 55 and Nasal Valve Collapse as primary contributor to NAO were treated. Follow-up visits occurred at week 1 and months 1, 3, 6, 12 and 18 post procedure. These visits included documentation of medical history, physical exam, NOSE score and digital photography. The NOSE scale is a validated as a Quality of Life (QOL) instrument¹⁸. It uses a 20-point scale to capture severity of breathing symptoms, with higher scores indicating more severe symptoms than lower scores. The results are converted to 100-point scale by multiplying the total score by five.

There was a total of five (5) device-related adverse events reported in four (4) subjects. These events included 1 case of hematoma, 1 case of inflammation, and 3 Implant retrievals. All events resolved with no clinical sequelae. Investigators concluded that the 3 Implant retrievals were the result of suboptimal implantation methods or possible significant patient lateral wall manipulation during the first post-operative week and were not caused by adverse physiologic tissue rejection or infection. The Implant placement procedure was revised during the course of the study to address suboptimal implantation techniques and no further retrieval events occurred.

To date, all follow up visits through 18 months have been completed; 15 out of 30 subjects completed 18 months of follow up. Three subjects have had other nasal surgery procedures and consequently exited the study; two subjects after the 12 month visit and one subject after the 18 month visit.

		Score	Change from baseline			Change from baseline % Change from baseline			Change from baseline	
Visit	N	Mean (SD)	Mean (SD)	LS Mean (95% CI)	p-value	Mean (SD)	LS Mean (95% Cl)	p- value		
1 Week	30	24.2 (16.14)	-52.5 (22.77)	-52.7 (-58.83, -46.55)	<.001	-67.2 (21.34)	-67.2 (-74.98, -59.51)	<.001		
1 Month	30	27.0 (23.95)	-49.7 (25.56)	-49.9 (-58.79, -40.93)	<.001	-64.8 (29.09)	-64.9 (-75.92, -53.86)	<.001		
3 Months	29	28.4 (26.90)	-48.4 (27.84)	-47.9 (-57.85, -37.96)	<.001	-63.4 (34.45)	-62.7 (-75.70, -49.66)	<.001		
6 Months	30	33.3 (29.69)	-43.3 (31.28)	-43.5 (-54.61, -32.44)	<.001	-56.2 (37.85)	-56.3 (-70.46, -42.07)	<.001		
12 Months	29	35.2 (29.17)	-40.9 (31.23)	-39.7 (-51.22, -28.11)	<.001	-53.1 (40.64)	-51.6 (-67.07, -36.12)	<.001		
18 Months	15	38.0 (33.32)	-41.7 (36.24)	-40.7 (-55.01, -26.30)	<.001	-51.3 (41.76)	-52.2 (-70.59, -33.87)	<.001		

A longitudinal summary of NOSE score is provided in the table below and these results demonstrate significant improvements over baseline for all time points measured.

This first in man study demonstrated the safety and effectiveness of the absorbable Implant to provide lateral cartilage support in patients with NVC as primary contributor to NAO.

2.3. POTENTIAL RISKS AND BENEFITS

2.3.1. NON-SIGNIFICANT RISK RATIONALE

This is a Non-Significant Risk ("NSR"), post-marketing study and will be conducted in accordance with the requirements prescribed in 21 CFR §812.2(b). Because it is a post-market evaluation of a 510(k) cleared medical device in commercial distribution, used according to FDA cleared indications for use, investigational device labeling described under §812.2(b) is not required.

Spirox Latera™ implant support of lateral wall cartilage (LATERAL-OR) study	Version 2.0
SPI-CP-301	September 7, 2017

This evaluation of the Spirox Latera[™] Absorbable Nasal Implant and Delivery Device is considered a NSR device study for the following reasons:

- While the device is an Implant, it does not present a potential for serious risk to the health, safety, or welfare of a subject;
- The device is not purported or represented to be used for supporting or sustaining human life;
- The device is not intended for a use of substantial importance in diagnosing, curing, mitigating, or treating disease or otherwise preventing impairment of human health; and,
- The device does not otherwise present a potential for serious risk to the health, safety or welfare of the subject.

See Appendix II for additional information supporting the rationale for a Non-Significant Risk determination.

2.3.2. KNOWN POTENTIAL RISKS

In patients with nasal airway obstruction, three factors may influence a decrease in the cross-sectional area of the nasal passage: (1) deviated septum, (2) enlarged turbinates, and (3) collapsed lateral wall. If all three etiologies are present, the surgeon would offer a treatment that would address all three. Thus, the subjects may undergo Implant placement in conjunction with septoplasty and/or inferior turbinate reduction procedures.

Both septoplasty and turbinectomy procedures are standards of care for the treatment of nasal airway obstruction. In the US alone, there are at least 340,000 of these procedures completed each year. The frequency of peri-operative adverse events is low, with an overall admittance rate of hospitalization of 0.85%. The most common reason for readmissions is hemorrhage¹⁹. Possible risks and complications for each procedure are described below.

Septoplasty procedure risks may include:

- Infections
- Nasal bleeding that may require surgical intervention or nasal packing
- Numbness of the nose, cheeks, and upper lip
- Bruising and swelling of the nose, eyelids, and upper lip
- Scarring, septal perforations, nose shape change including "saddle nose" deformity and nostril asymmetry
- A decreased sense of smell
- General anesthesia effect
- Pain and discomfort in the nose, particularly at the front
- Continued nasal obstruction
- Nasal crusting
- Cerebrospinal fluid leak
- Death

The following complication rates have been reported after septoplasty²⁰:

- Infections 3%
- Hematomas 2-7%
- Septum perforations 3-25%
- Changes in nose shape -5-60%
- Smelling disorders less than 1%

Spirox Latera™ implant support of lateral wall cartilage (LATERAL-OR) study	Version 2.0
SPI-CP-301	September 7, 2017

Turbinate reduction procedure risks may include:

- Mild-to-moderate edema with subsequent nasal obstruction and thick mucus formation
- If mucosal erosion is present, the risk of postoperative bleeding and adherent crust formation increases
- Scar tissue (synechiae) may form between the turbinate and the septum
- Bleeding requiring further intervention
- Empty nose syndrome

The following complication rates have been reported after turbinate reduction:

• Synechiae rates up to 36%²⁰.

Latera[™] implant procedure risks may include:

- Inflammatory foreign body reaction, foreign body sensation, pain or discomfort, infection, and extrusion
- Excessive activity, trauma, or loading may lead to bending, fracture, loosening, and/or migration of the Implant
- Implants placed near the skin surface may be palpable or cause skin irritation
- Temporary hematoma from cannula insertion
- Implant retrieval, defined as surgeon initiated removal of implant not associated with body rejection of implant
- Unintended perforation of the skin

Risks related to the Latera Implant will be mitigated throughout the course of the study by investigator training, study monitoring and follow up evaluations. The training related to device placement will be provided to the investigators by the sponsor in a clinically relevant model prior to device use in clinic. Only procedure-trained investigators that are authorized by the sponsor will be allowed to place the devices during the study. In addition, prior to initiation of enrollment, procedure-trained investigators will have completed a number of commercial cases.

Monitoring and follow up will ensure that adverse events are being reported in a timely manner and shared with the principal investigators and members of the research team. Corrective action will be immediately taken if untoward trends are observed with a particular investigator.

2.3.3. KNOWN POTENTIAL BENEFITS

The Latera[™] Absorbable Nasal Implant is indicated to support upper and lower lateral nasal cartilage. The prior investigation described in Section 2.2, demonstrated that the device reduced nasal obstruction symptoms by 53.1 % at 12 months in patients with nasal valve collapse as primary contributor to NAO (no septal or turbinate treatment). For subjects requiring lateral cartilage support that also have deviated septum and enlarged turbinates, it is expected that the Latera Implant may provide additional benefit to the subjects who are also undergoing concurrent septoplasty and/or turbinate procedures. In addition, subjects may benefit from the additional clinical monitoring and follow-up evaluations required by this study protocol.

3. OBJECTIVES AND PURPOSE

The objective of the LATERAL-OR study is to obtain outcomes data in subjects with severe to extreme¹⁷ class NOSE scores undergoing placement of the Spirox Latera Implant with or without concurrent septoplasty and/or turbinate reduction procedures in an operating room setting.

4. STUDY DESIGN AND ENDPOINTS

4.1. DESCRIPTION OF THE STUDY DESIGN

This is a prospective, multi-center, non-randomized, single arm controlled study. It is a post-market evaluation of a 510(k) cleared, non-significant risk, medical device in commercial distribution, used according to FDA cleared indications for use. Each subject serves as his or her own control.

4.2. STUDY ENDPOINTS

4.2.1. PRIMARY ENDPOINTS

Primary Efficacy Endpoint: Proportion of treatment responders at 6 months post procedure.

• Responder is defined as subject that has at least 1 NOSE class improvement or at least 20% NOSE score reduction

Primary Safety Endpoint: Nasal procedure and Latera device-related adverse events through 6 months.

4.2.2. SECONDARY ENDPOINTS

- 1. Proportion of treatment responders at 1, 3, 12, 18 and 24 months post procedure.
- 2. Change in nasal airway obstruction from baseline to 1,3, 6,12, 18 and 24 months as reported by subjects on the VAS scale.
- 3. Subject satisfaction questionnaire at 6 months.
- 4. Procedure and device-related adverse events though 24 months.

4.2.3. EXPLORATORY ENDPOINTS

Exploratory endpoints for informational purposes only:

- 1. Index procedure resource utilization: Anesthesia, procedure time and time to discharge.
- 2. Follow up resource utilization: Nasal airway obstruction related return visits and medication utilization.
- 3. Subject satisfaction questionnaire at 1, 3 and 12 months.
- 4. Degree of nasal way obstruction as reported by subjects on the VAS scale at baseline with decongestant use.
- 5. Endoscopic lateral wall insufficiency score per side²¹ at baseline and 6 months
- 6. 3-D camera lateral wall motion assessment per side at baseline and 3, 6 and 12 months (at select sites).
- 7. Cosmesis changes from baseline evaluated by Independent Photo Review 3 and 6 months (at select sites).
- 8. Allergic rhinitis status at 1, 3, 6 and 12 months.
- 9. Nasal geometry: length of nose, height and width of nose, skin thickness of lateral wall at baseline.
- 10. Type of turbinate procedure.

5. STUDY ENROLLMENT AND WITHDRAWAL

5.1. PARTICIPANT INCLUSION CRITERIA

In order to be eligible to participate in this study, an individual must meet all of the following inclusion criteria:

- 1. The subject has NOSE Score \geq 55.
- 2. The subject has dynamic lateral nasal wall insufficiency as confirmed by positive Modified Cottle Maneuver.
- 3. The subject is ≥ 18 years of age.
- 4. The subject is willing and able to provide informed consent and comply with the study protocol.
- 5. The subject is seeking treatment for nasal airway obstruction due to Nasal Valve Collapse (NVC) and is willing to undergo nasal Implant procedure alone or with septoplasty and/or a turbinate reduction procedure in an operating room setting.
- 6. The subject has appropriate nasal and facial anatomy to receive Latera Implant.
- 7. The subject agrees to follow-up examinations through twelve (12) months post operatively.
- 8. The subject has failed to benefit from appropriate maximal medical management [e.g., nasal steroids (at least 4 weeks); antihistamines; oral decongestants; nasal strips, stents, or cones]. Failure of maximal medical management may be from lack of effectiveness or inability of subject to tolerate.

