5.3. STRATEGIES FOR RECRUITMENT AND RETENTION

A maximum of 170 subjects will be enrolled in the study to reach target of 150 subjects completing the 24 Month follow-up post-procedure. It is anticipated that this enrollment will take place in the initial 8 months of the study after study start-up. Subjects will be enrolled at approximately 25 individual sites within the United States.

Subjects will be recruited from sites' existing patient populations that are seeking treatment for nasal airway obstruction including nasal valve collapse. Anatomical considerations may impact the race distribution (e.g. some races may be less prone to lateral wall collapse), but the intention is to enroll all eligible subjects. Based on an earlier study with the device, both genders are expected to be well represented in the study.

Study brochures containing information on study participation and the Implant may be provided to the sites, as well as posters that may be displayed either as hard copies or electronically on computer monitors in the office.

The following tools will be utilized to encourage subjects' compliance to the study visit schedule:

- Subjects will receive a stipend for their time and to cover travel costs as follows: Subjects who complete the study are eligible for a total stipend of up to \$700 to be paid over a two year period. Upon completion of the Baseline, 1 Month, 3 Month, 6 Month,12 Month, 18 Month and 24 Month visits, subjects will receive a \$100 prepaid debit card at each visit or follow up. The 18 Month and 24 Month follow up evaluations will be conducted in one of the following manners: office visit, telephone interview, or completion of form by subject and mailed to office for data entry, depending on subject availability.
- Additionally, subjects will be contacted by phone, and where available automated texting and email, for both reminders to schedule or confirm upcoming study visits and as reminders for visits that have already been scheduled.

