7.7. STUDY SCHEDULE OF EVENTS TABLE

Study Events	Screening & Enrollment (Visit 1)	Baseline Evaluation (Visit 2) ¹	Treatment (Visit 3)	Follow Up 1 mo (Visit 4)	Follow Up 3 mo (Visit 5)	Follow Up 6 mo (Visit 6)	Follow Up 12 moStudy Visit (Visit 7)	Follow Up 18 & 24 mo/Final Study Visit (Visits 8 & 9)	Early Exit
Secure Informed Consent	Х								
Secure Re-Consent for 18M and 24M Follow Up							Х		
Inclusion/Exclusion	Х		X ²						
NOSE Scale (PRO) ³	Х	Х	X ²	Х	Х	Х	Х	Х	
NAO Breathing Assessment (PRO)		Х		Х	Х	Х	Х	Х	
Subject Satisfaction Questionnaire (PRO)				Х	Х	Х	Х		
Health Economics Questionnaire (PRO)		Х		Х	Х	Х	Х		
Nasal Medical History/Nasal Geometry		Х							
Nasal Exam		Х		Х	Х	Х	Х		
Lateral Wall Motion Video		Х				Х			
Photography- 3D Camera (select sites)		Х			Х	Х	Х		
Photography –Cosmetic (select sites)		Х			Х	Х			
Turbinate Hypertrophy Contribution to		Х							
NAO assessment (Nasal Decongestant)									
Photography – Planning Images			Х						
NAO Treatment			Х						
Concomitant Medications		Х	Х	Х	Х	Х	Х		
Adverse Event Assessment			X	X	X	X	Х		Х
Adverse Device Effects Assessment								X	
Complete Study Exit Form								X ⁴	Х

¹ Visit 2 activities may be done in conjunction with Study Visit 1. In this instance, the Screening NOSE Scale is not required.

² If Visit 3 (Treatment Visit) is more than 1 month after Visit 1, inclusion/exclusion criteria need to be re-confirmed. Additionally, subjects should be asked to review IC form, initial and date the IC document to confirm continued consent for participation, and complete NOSE scale.

³ If Visits 1, 2 and 3 are done on the same day, the Screening and Treatment NOSE Scales are not required.

⁴To be completed at 24M follow up.

Spirox Latera™ implant support of lateral wall cartilage (LATERAL-OR) study	
SPI-CP-301	Sep

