10.5. SAMPLE SIZE

The primary study hypothesis is a superiority comparison to a target proportion:

Null Hypothesis H₀: the proportion of responders at 6 months is =0.50, versus Alternative Hypothesis H_A: the proportion of responders at 6 months is \neq 0.50

See section 10.4.2 for the definition of response. This hypothesis will be evaluated using an exact test.

In order to have > 90% power to rule out a response rate \leq 50% at a 5% (2-sided) significance level, assuming a true response rate of 66%, 150 subjects with 6 month follow-up are needed. Assuming about 10% drop-out rate, up to 170 subjects will be enrolled. All mITT subjects will be used for this comparison, regardless of protocol deviations.

The assumed response rate is the minimum value expected to be consistent with previous trials, where an 80% response rate at 6 months was observed.

Sample size calculations were performed using the package RCTDesign for R version 3.2.3.

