### SAMPLE SIZE JUSTIFICATION

The primary statistical hypothesis will be evaluated using an exact test. In order to have > 90% power to rule out a response rate  $\leq$  50% at a 5% (2-sided) significance level, assuming a true response rate of 66%, 120 subjects with 6 months of follow-up are needed. Assuming a 20% drop-out rate, at least 150 subjects (and up to 170 subjects) will be enrolled. A 66% response rate is the minimum response rate that is consistent with a previous trial, where an 80% response rate at 6 months was observed.

Sample size calculations were performed using the package RCTDesign for R, version 3.2.3.

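### Inclusion 7 still secures agreement to only 12 months of follow-up in a 24-month study, and re-consent for months 18 and 24 is scheduled only at month 12 without saying whom it covers

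*Protocol*

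**What the plan says.** Entry commitment (Protocol 5.1). Inclusion 7: "The subject agrees to follow-up examinations through twelve (12) months post operatively". Inclusion 4 is general and names no duration: "The subject is willing and able to provide informed consent and comply with the study protocol".

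Duration of the study. The Protocol Summary states: "Enrolled subjects will be followed for 24 months post-procedure". Section 4.2.2 sets secondary endpoints at months 18 and 24 (response, VAS change) and through month 24 (adverse events). Section 7.1.4 ends participation at the 24-month follow-up.

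Retention target (Protocol 5.3): "A maximum of 170 subjects will be enrolled in the study to reach target of 150 subjects completing the 24 Month follow-up post-procedure".

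Consent for the extension. The schedule in 7.7 has a row "Secure Re-Consent for 18M and 24M Follow Up", marked at the 12-month visit (Visit 7) and nowhere else. Neither the row nor its footnotes say which subjects it applies to. Appendix I shows that the 18- and 24-month evaluations were added in September 2017, while the protocol was first released in July 2016.

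Sample size (Protocol 10.5): "150 subjects with 6 month follow-up are needed", and "Assuming about 10% drop-out rate, up to 170 subjects will be enrolled". The SAP's sample size section instead says "120 subjects with 6 months of follow-up are needed", with 20% drop-out.

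**The concern.** The amendment lengthened follow-up from 12 to 24 months, but the entry criterion that names a duration was left at 12. The only scheduled request for the additional year comes at the visit where the subject has just rated the 12-month result. The study is open label (Protocol 10.6), and NOSE and VAS are completed by the subject. Someone whose consent runs to 12 months therefore chooses whether to continue with the outcome in view.

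Two things are at stake. The first is numbers: the 24-month target uses the same 170 and 150 as the 6-month calculation, so nothing is set aside for refusals. The second is representativeness: if continuing depends on how well the nose works at month 12, those observed at months 18 and 24 need not resemble those treated. These are the only follow-ups at or after the implant's stated absorption time of about 18 months (Protocol 6.2). The planned comparison of subjects with and without data covers the 6-month NOSE score only (Protocol 10.4.5).

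**Working it through.** **1. The plan's own figures, reproduced as a 6-month calculation.** Inputs from Protocol 10.5: null 0.50, true response 0.66, two-sided 5%, n = 150, about 10% drop-out.
- Exact binomial, n = 150: success at 88 or more responders, upper-tail error 0.0204, power 97.5%. This agrees with the stated power above 90%.
- Inflation: 150 / (1 − 0.10) = 166.7, so 167, close to the stated 170.
- SAP variant, n = 120: success at 72 or more, power 93.0%; 120 / (1 − 0.20) = 150, as stated.

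The 150 and 170 are thus explained by month 6 alone.

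**2. The same figures read as a 24-month target (Protocol 5.3).** Total permitted loss is 170 − 150 = 20, and 20/170 = 11.8%. This needs no assumption.

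**3. Room left for the extension decision.** Required share continuing after month 12 = 150 / [170 × (1 − loss by month 12)]. The documents give no loss rate for month 12, so a range is shown.

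| Assumed loss by month 12 | Remaining | Share that must continue to month 24 |
|---|---|---|
| 0% | 170 | 88.2% |
| 5% | 161.5 | 92.9% |
| 10% | 153 | 98.0% (3 may be lost) |
| 20% | 136 | 150 cannot be reached |

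The 10% and 20% rows borrow the protocol's and the SAP's drop-out rates, which both documents attach to the 6-month sample size. They are illustrations.

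**4. Completers if some decline.** With 153 at month 12 and assumed continuation of 95%, 90% and 80%: 153 × 0.95 = 145, 153 × 0.90 = 138, 153 × 0.80 = 122.

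**5. Effect on precision.** Approximate 95% half-width at 66% response = 1.96 × √(0.66 × 0.34 / n). For n = 150 it is 7.6 points; for n = 122 it is 8.4 points.

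**6. Effect of outcome-related continuation.** Observed rate = p·a / [p·a + (1 − p)·b], where p is the true 24-month response and a and b are the assumed continuation rates of responders and non-responders. Take p = 0.66.
- a = 0.95, b = 0.75: 0.627 / (0.627 + 0.255) = 71.1%, with 153 × 0.882 = 135 completers.
- a = 0.75, b = 0.95: 0.495 / (0.495 + 0.323) = 60.5%, with 153 × 0.818 = 125 completers.
- Equal rates: no bias, only fewer subjects.

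The direction cannot be predicted from the documents. Under these assumptions selection shifts the rate by about 5 points either way, whereas in step 5 the half-width widens by less than 1 point.

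**The case against.** The other side has substance on several points.

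- **A subject could enter while planning to leave at month 12.** A reader might infer this from inclusion 7. The documents do not support it: inclusion 4, and the consent step in 7.1.1, require willingness to comply with the protocol, which runs to 24 months. What stands is that the only criterion naming a duration names the wrong one.
- **The wording may be literal.** Inclusion 7 speaks of examinations, and nasal exams do stop at month 12 (7.1.4, 7.7); months 18 and 24 can be done by telephone or mail (5.3). On that reading the criterion is not false, but it is still silent on the last two follow-ups.
- **Re-consent is proper.** Subjects who entered before September 2017 agreed to less and must be asked, and 13.2 provides for deciding who is re-consented. With enrolment expected to take 8 months, many may be in this group; actual dates are not given. This supports having the row. It does not support leaving its scope open or asking only at month 12.
- **The consent form may already cover 24 months.** It is not available for review, so its content cannot be asserted either way. A claim that the whole 150 target depends on a second opt-in therefore goes too far.
- **A missed Visit 7 does not end the matter.** A reader might infer that such a subject is never asked. Nothing bars a later request; there is only no planned one.
- **The margin of 3 subjects (2.0%) is not the protocol's own figure.** Section 10.5 ties the 10% to 6-month follow-up.
- **Consequences are limited.** Months 18 and 24 carry no formal hypothesis (10.2), are supportive (10.4.9) and descriptive (SAP 4.1.1).

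**Conclusion.** The inconsistency is in the current text and is worth correcting. Inclusion 7 covers 12 months of a 24-month study, and the re-consent row has neither a defined group nor a planned opportunity before month 12. The firm figure is the total allowance: 20 losses among 170 (11.8%) over 24 months, with none set aside for refusal. Everything tighter than that rests on an assumed loss before month 12, and the completer counts and shifts in response rate rest on assumed continuation rates.

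Outcome-aware choice is an inference from the open-label design and the timing of the request. It applies to subjects whose consent ends at 12 months; for those enrolled under the current version it depends on a consent form that is not shown. The primary 6-month endpoint and its power are untouched. The exposure is to the precision and representativeness of the supportive 18- and 24-month results.

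**What to change.** 1. In Protocol 5.1, change inclusion 7 to 24 months for anyone enrolled under the current version, and confirm that their main consent covers months 18 and 24.
2. In 7.7, limit the re-consent row to subjects who consented under earlier versions. Seek it at the next scheduled contact after IRB approval, with month 12 as the last planned opportunity.
3. In 5.3, state separately what retention and re-consent the 24-month target assumes, since 10.5 supports 150 and 170 for month 6 only.

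The cost is one criterion, a check of the consent form, one schedule row and a sentence in 5.3. A few candidates may decline the longer commitment at entry, although remote follow-up at months 18 and 24 makes it light. Subjects may still withdraw at any time (5.4) and know their own results, so the change reduces outcome-related loss but does not remove it. Tabulating month-12 NOSE and VAS by whether subjects continued would show how much remains, using data already collected.
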